9.4.4 SAFETY ANALYSES

At six-month intervals, the Biostatistician on the study will test whether there are significant differences between those in the active E2 versus placebo E2 for moderate or severe AEs. The statistical analysis method will be a two-sided Fisher exact Test, with alpha = 0.05. These results will be provided to the Data Safety and Monitoring Board (DSMB) along with the summary report of enrollment and other safety data. The DSMB will consider stopping the study based on the results of the statistical tests and other safety data.

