4 STUDY DESIGN

4.1 OVERALL DESIGN

- Hypothesis: Our central hypothesis is that stabilization of E2 variability, not increasing E2 levels, will modify HPA axis stress activation and in turn, beneficially modify cognitive bias towards perceived threat and approach motivation, thereby decreasing anxiety and anhedonia.
- Phase: N/A
- Design of trial: randomized, placebo-controlled, double-blinded parallel design.
- Study arms: 2 (active and placebo)
- Single site study
- Methods to minimize bias: Under double-blind procedures, subjects will be randomized to receive transdermal E2 or placebo for 16 weeks. The study biostatistician will create the randomization scheme and UNC Investigational Drug Services will manage the randomization and dispensing of hormones in blinded form.
- Intervention and Dosing: Subjects randomized to active treatment arm will wear a patch delivering 0.10mg of E2 over 24 hours and will take oral micronized progesterone (200mg/daily) for 12 days at two points in the intervention. Subjects randomized to placebo arm will wear placebo patches and take placebo pills matching in appearance.
- Planned Interim Analysis: Data and Safety Monitoring Board will monitor the safety of the study every six months. The DSMB will evaluate issues of participant safety as well as enrollment information and the adequacy and integrity of accumulating data

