7 STUDY INTERVENTION DISCONTINUATION AND PARTICIPANT DISCONTINUATION/WITHDRAWAL

7.1 DISCONTINUATION OF STUDY INTERVENTION

At six-month intervals, the Biostatistician on the study will test whether there are significant differences between those in the active E2 versus placebo E2 for moderate or severe AEs. The statistical analysis method will be a two-sided Fisher exact Test, with alpha = 0.05. These results will be provided to the Data Safety and Monitoring Board (DSMB) along with the summary report of enrollment and other safety data. The DSMB will consider stopping the study based on the results of the statistical tests and other safety data.

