8.3.3 CLASSIFICATION OF AN ADVERSE EVENT

8.3.3.1 SEVERITY OF EVENT

The following guidelines will be used to describe severity of AEs.

- **Mild** – is defined as having no effect on activities of daily living such as transient light headedness or sweating with venipuncture; breast tenderness, mild skin irritation; or something of equal significance that requires no medical intervention and is of marginal clinical relevance.
- **Moderate** – would be associated with temporary (minutes to a few days) disruption in activities of daily living such as temporary loss of consciousness with venipuncture; a worsening of migraines or headache that require bed rest, an increase in anxiety or anhedonia symptoms consistent with clinically meaningful levels, emergent suicide intent without specific plan (severity level 4 on the C-SSRS), excess sleepiness or fatigue that resolves with additional rest, or something of equal significance.
- **Severe** – would cause serious disruption in daily activities of living and may or may not require hospitalization. Examples of such events would include a thromboembolic event, breast carcinoma, an increase in blood pressure consistent with Stage 2 hypertension, any cardiovascular event, any event that is permanently disabling, any event requiring hospitalization or is life threatening, severe mood impairment or emergent suicide ideation with specific plan (severity level 5 on the C-SSRS) or any suicidal behavior (actual attempt, interrupted attempt, aborted attempt, or preparation towards imminent suicide attempt), or something of equal significance. The development of endometrial hyperplasia with or without atypia would also be consistent with a severe AE.

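### The six-monthly safety comparison does not separate mood events from medical events, so a medical excess on estradiol can be diluted or offset

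*Combined protocol and SAP*

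**What the plan says.** Section 9.4.4, repeated in 7.1, sets the safety comparison. Every six months the biostatistician is to "test whether there are significant differences between those in the active E2 versus placebo E2 for moderate or severe AEs", by a "two-sided Fisher exact Test, with alpha = 0.05". The result goes to the DSMB with enrolment and other safety data, and "The DSMB will consider stopping the study based on the results of the statistical tests and other safety data". Section 9.4.6 only refers back to 9.4.4.

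Section 8.3.3.1 decides what enters the comparison. Moderate events include "an increase in anxiety or anhedonia symptoms consistent with clinically meaningful levels". Severe events include "severe mood impairment or emergent suicide ideation with specific plan", alongside "a thromboembolic event, breast carcinoma, an increase in blood pressure consistent with Stage 2 hypertension, any cardiovascular event" and endometrial hyperplasia. Neither 7.1 nor 9.4.4 divides the comparison by type of event.

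Anxiety (STAI) and anhedonia (SHAPS) are the two primary endpoints (section 3). Section 8.3.4 has staff watch the same two scales for increases of more than 50% from baseline as part of event monitoring. The central hypothesis in 4.1 is that stabilising estradiol modifies stress activation, threat bias and motivation, "thereby decreasing anxiety and anhedonia".

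**The concern.** The natural reading of 7.1 and 9.4.4 is a count, per arm, of women with any moderate or severe event. That count mixes two kinds of event which the trial's own hypothesis expects to move in opposite directions: medical side effects, which could rise on estradiol, and worsening anxiety or anhedonia, which should fall. A single comparison nets one against the other. Dilution does not need a benefit: mood events at the same rate in both arms add noise to a medical difference.

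At stake is the one prespecified statistic that the plan names as an input to stopping. It can be unremarkable when estradiol is causing medical harm, and it can be significant when the only difference is fewer mood events on estradiol.

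**Working it through.** **Inputs from the plan.** Two-sided Fisher exact test at 0.05 (9.4.4); 60 women per arm (4.2 and 6.3). As a sensitivity case, the 138 women in 9.2 give 138 / 2 = 69 per arm. The plan states no power for this test and no rates of moderate or severe events, so there is no figure to reproduce.

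**Assumed.** All event rates below; independence of the two event types within a woman; one look with full arms.

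**Method.** Combined rate per arm = 1 − (1 − medical rate)(1 − mood rate). Power is exact: the two binomial probabilities are multiplied and summed over every pair of counts where the Fisher p-value is at most 0.05 and the estradiol arm has more events.

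For example, medical events of 25% vs 5% with mood events of 5% vs 20% give 1 − 0.75 × 0.95 = 28.75% on estradiol and 1 − 0.95 × 0.80 = 24% on placebo.

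| Medical, E2 vs placebo | Mood, E2 vs placebo | Combined, E2 vs placebo | Power, medical only | Power, combined |
|---|---|---|---|---|
| 25% vs 5% | 10% vs 10% | 32.5% vs 14.5% | 85% | 57% |
| 25% vs 5% | 5% vs 15% | 28.75% vs 19.25% | 85% | 17% |
| 25% vs 5% | 5% vs 20% | 28.75% vs 24% | 85% | 6% |
| 20% vs 5% | 10% vs 10% | 28% vs 14.5% | 63% | 35% |
| 20% vs 5% | 5% vs 15% | 24% vs 19.25% | 63% | 6% |
| 15% vs 5% | 11% vs 5% | 24.35% vs 9.75% | 33% | 48% |

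With 69 per arm the first row becomes 90% and 65%, and the second 90% and 20%.

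**The same thing in counts.** Medical events in 12 of 60 women on estradiol and 3 of 60 on placebo give p = 0.025. If 6 further women on estradiol and 15 further on placebo have mood worsening only, the totals are 12 + 6 = 18 and 3 + 15 = 18, and p = 1.0.

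**Benefit alone.** With medical events of 5% in both arms and mood events of 5% vs 25%, the combined rates are 1 − 0.95 × 0.95 = 9.75% and 1 − 0.95 × 0.75 = 28.75%. The test is then significant 69% of the time, always in the direction of fewer events on estradiol.

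**The opposite case.** The last table row assumes that mood events are also more frequent on estradiol. Combining the classes then raises power, from 33% to 48%.

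**The case against.** **The size is a matter of assumption.** This stands. A medical rate of 25% vs 5% is not taken from the plan. Section 8.3.3.1 grades breast tenderness and mild skin irritation as mild, so those common effects never enter the test, and section 2.3.1 describes serious events as very unlikely. With medical events of 10% vs 5%, the medical-only test at 60 per arm has 9% power; with 5% vs 1% it has 5%. At an early look with 20 per arm, even 25% vs 5% is detected only 30% of the time. Separation does not rescue the test for small or rare harms.

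**The DSMB has other routes.** This also stands. Under 10.1.6 it monitors medical and psychological events, chooses its own tables and sees recorded side effects. Severe events reach it within a week (8.3.5). A reader might infer that a masked test would leave harm unseen; the documents do not support that. The weakness lies in the prespecified statistic, not in oversight as a whole.

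**Pooling is inferred.** Sections 7.1 and 9.4.4 never say that there is one composite, and they speak of tests in the plural. The plural may refer only to the repeated looks, and no split is described, so pooling remains the natural reading.

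**Mood worsening may be a drug effect.** Section 2.3.1 lists depression and nervousness in 11% of estradiol users, and 8.3.1 defines adverse events regardless of cause. This rules out the tempting remedy of taking mood events out of the arm comparison.

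**Two stronger readings fail.** A reader might infer that mood worsening is the expected course on placebo. Section 2.1 supports a raised population risk, but its 25% is the share of women impaired, not a rate of new worsening, and H1 in 9.1 expects no significant mean change on placebo. Individual worsening can still occur with a stable mean. A reader might also infer that separation stops the safety review from showing the tail of the primary outcome by arm. It does not: a mood comparison shows it more directly, and psychological deterioration is already within the DSMB's remit.

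**Conclusion.** The point holds as a weakness of the safety statistic. The definitions in 8.3.3.1 and the comparison in 7.1 and 9.4.4 together put worsening of the primary-outcome constructs into the same tested category as medical harm. The direction of the problem follows from the plan's own hypothesis, and dilution at equal mood rates needs no benefit at all. The size is illustrative only: it rests on assumed rates, independent event types and one look at full enrolment. The DSMB's wider access to data and its freedom to depart from the test make this a worthwhile low-cost improvement rather than a flaw in the trial's safety oversight.

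**What to change.** In 7.1 and 9.4.4, prespecify the by-arm comparison separately for (a) medical moderate or severe adverse events and (b) moderate or severe events of mood, anxiety, anhedonia or suicidality. Give both to the DSMB at each review, optionally with the combined count, which is useful if both classes move against estradiol. Keep class (b) in a formal comparison and do not reduce it to a listing. If separate tests are already intended, one sentence in each section settles the matter.

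The cost is wording in two sections and one further comparison from data already collected. Event definitions, visits and sample size are unchanged. The downside is one more test per review. With each test at 0.05, the chance of at least one false signal per review is bounded by 0.05 + 0.05 = 0.10 instead of 0.05. That is acceptable for a board that weighs the tests with other data and is not bound by them.

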9.4.5 BASELINE DESCRIPTIVE STATISTICS

The two intervention arms will be compared on baseline (week 8) characteristics in the SHAPS score, the State-Trait Anxiety Inventory score, the EEfRT and Dot Probe scores, and the Cortisol AUC. Differences between the two groups will be compared using inferential statistics (student t-Tests).

9.4.6 PLANNED INTERIM ANALYSES

See section 9.4.4 for details on safety analysis.

9.4.7 SUB-GROUP ANALYSES

The study intervention (transdermal estradiol patch and micronized progesterone pill) is only for use in women. Therefore, no sub-group analyses will be performed.

9.4.8 TABULATION OF INDIVIDUAL PARTICIPANT DATA

Not applicable

9.4.9 EXPLORATORY ANALYSES

Not applicable

10 SUPPORTING DOCUMENTATION AND OPERATIONAL CONSIDERATIONS

10.1 REGULATORY, ETHICAL, AND STUDY OVERSIGHT CONSIDERATIONS

10.1.1 INFORMED CONSENT PROCESS

10.1.1.1 CONSENT/ASSENT AND OTHER INFORMATIONAL DOCUMENTS PROVIDED TO PARTICIPANTS

Consent forms describing in detail the purpose of the study, study intervention, study procedures, and risks are given to the participant and written documentation of informed consent is required prior to starting intervention/administering study intervention.

10.1.1.2 CONSENT PROCEDURES AND DOCUMENTATION

Informed consent is a process that is initiated prior to the individual's agreeing to participate in the study and continues throughout the individual's study participation. Consent forms will be Institutional Review Board (IRB)-approved and the participant will be asked to read and review the document. The investigator will explain the research study to the participant and answer any questions that may arise. A verbal explanation will be provided in terms suited to the participant's comprehension of the purposes, procedures, and potential risks of the study and of their rights as research participants. Participants will have the opportunity to carefully review the written consent form and ask questions prior to signing. The participants should have the opportunity to discuss the study with their family or surrogates or think about it prior to agreeing to participate. The participant will sign the informed consent document prior to any procedures being done specifically for the study. Participants must be informed that participation is voluntary and that they may withdraw from the study at any time, without prejudice. A copy of the informed consent document will be given to the participants for their records.

The informed consent process will be conducted and documented in the source document (including the date), and the form signed, before the participant undergoes any study-specific procedures. The rights and welfare of the participants will be protected by emphasizing to them that the quality of their medical care will not be adversely affected if they decline to participate in this study.

10.1.2 STUDY DISCONTINUATION AND CLOSURE

This study may be temporarily suspended or prematurely terminated if there is sufficient reasonable cause. Written notification, documenting the reason for study suspension or termination, will be provided by the suspending or terminating party to study participants, investigator, funding agency, and regulatory authorities. If the study is prematurely terminated or suspended, the Principal Investigator (PI) will promptly inform study participants, the Institutional Review Board (IRB), and sponsor and will provide the reason(s) for the termination or suspension. Study participants will be contacted, as applicable, and be informed of changes to study visit schedule.

Circumstances that may warrant termination or suspension include, but are not limited to:

- Determination of unexpected, significant, or unacceptable risk to participants
- Demonstration of efficacy that would warrant stopping
- Insufficient compliance to protocol requirements
- Data that are not sufficiently complete and/or evaluable
- Determination that the primary endpoint has been met
- Determination of futility

Study may resume once concerns about safety, protocol compliance, and data quality are addressed, and satisfy the sponsor, IRB and/or Food and Drug Administration (FDA).

10.1.3 CONFIDENTIALITY AND PRIVACY

Participant confidentiality and privacy is strictly held in trust by the participating investigators, their staff, and the sponsor(s) and their interventions. This confidentiality is extended to cover testing of biological samples and genetic tests in addition to the clinical information relating to participants. Therefore, the study protocol, documentation, data, and all other information generated will be held in strict confidence. No information concerning the study, or the data will be released to any unauthorized third party without prior written approval of the sponsor.

All research activities will be conducted in as private a setting as possible.

The study monitor, other authorized representatives of the sponsor, representatives of the Institutional Review Board (IRB), regulatory agencies or pharmaceutical company supplying study product may inspect all documents and records required to be maintained by the investigator, including but not limited to, medical records (office, clinic, or hospital) and pharmacy records for the participants in this study. The clinical study site will permit access to such records.

The study participant's contact information will be securely stored at each clinical site for internal use during the study. At the end of the study, all records will continue to be kept in a secure location for as long a period as dictated by the reviewing IRB, Institutional policies, or sponsor requirements.

Study participant research data, which is for purposes of statistical analysis and scientific reporting, will be transmitted to and stored in the study database. This will not include the participant's contact or identifying information. Rather, individual participants and their research data will be identified by a unique study identification number. The study data entry and study management systems used by clinical sites and by research staff will be secured and password protected. At the end of the study, all study databases will be de-identified and archived at the research site.

To further protect the privacy of study participants, a Certificate of Confidentiality will be issued by the National Institutes of Health (NIH). This certificate protects identifiable research information from forced disclosure. It allows the investigator and others who have access to research records to refuse to disclose identifying information on research participation in any civil, criminal, administrative, legislative, or other proceeding, whether at the federal, state, or local level. By protecting researchers and institutions from being compelled to disclose information that would identify research participants, Certificates of Confidentiality help achieve the research objectives and promote participation in studies by helping assure confidentiality and privacy to participants.

10.1.4 FUTURE USE OF STORED SPECIMENS AND DATA

Data collected for this study will be analyzed and stored at the research site. After the study is completed, the de-identified, archived data will be transmitted to and stored at the research site, for use by other researchers including those outside of the study. Permission to transmit data will be included in the informed consent.

With the participant's approval and as approved by local Institutional Review Boards (IRBs), de-identified biological samples will be stored at the research site with the same goal as the sharing of data with biospecimen repository. These samples could be used to research the factors that cause or contribute to the development of mood disorders in the menopause transition, its complications, and other conditions for which individuals in the menopause transition are at increased risk, and to improve treatment. The repository will also be provided with a code-link that will allow linking the biological specimens with the phenotypic data from each participant, maintaining the blinding of the identity of the participant.

During the conduct of the study, an individual participant can choose to withdraw consent to have biological specimens stored for future research. However, withdrawal of consent with regard to biosample storage may not be possible after the study is completed.

When the study is completed, access to study data and/or samples will be provided through the only personnel approved by the study investigator.

10.1.6 SAFETY OVERSIGHT

The safety of the study will be monitored by a Data and Safety Monitoring Board (DSMB). This will ensure the independent oversight of issues related to safety and adverse events. The North Carolina Translational and Clinical Sciences (NC TraCS) Data and Safety Monitoring Board (NC TraCS DSMB) will be used for this purpose. The Board is composed of MDs from a variety of disciplines, an R.N. from the UNC School of Nursing, a Biostatistician, a Regulatory Expert, and for purposes of this study, a psychiatrist or clinical psychologist will serve as an ad hoc member.

The NC TraCS DSMB will monitor for AEs, including medical events (e.g., VTEs) and psychological events (e.g., significant deterioration in anxiety or anhedonia symptoms and emergent suicidal intent or behavior). The DSMB will specify the tables and data it wishes to have presented to it at all meetings, including but not limited to, all side effects and symptoms recorded at the study visits (see Adverse Events Form) and all interim phone calls initiated by research subjects to report AEs or concerns. DSMB review of this study will occur every six months (or more frequently if specified by the DSMB). At these meetings, the DSMB will also review data from subjects who have withdrawn or dropped out of the study and the reasons for drop out. The DSMB will evaluate issues of participant safety as well as enrollment information and the adequacy and integrity of accumulating data. The DSMB will also identify if any study procedures should be altered or stopped in the event of an indication of harm to participants attributable to the study interventions.

10.1.7 CLINICAL MONITORING

Not applicable.

10.1.8 QUALITY ASSURANCE AND QUALITY CONTROL

The research site will perform internal quality management of study conduct, data and biological specimen collection, documentation and completion. An individualized quality management plan will be developed to describe a site's quality management.

Quality control (QC) procedures will be implemented beginning with the data entry system and data QC checks that will be run on the database will be generated. Any missing data or data anomalies will be communicated to the site for clarification/resolution.

Following written Standard Operating Procedures (SOPs), the monitors will verify that the clinical trial is conducted and data are generated and biological specimens are collected, documented (recorded), and reported in compliance with the protocol, International Conference on Harmonisation Good Clinical Practice (ICH GCP), and applicable regulatory requirements (e.g., Good Laboratory Practices (GLP), Good Manufacturing Practices (GMP)).

The investigational site will provide direct access to all trial related sites, source data/documents, and reports for the purpose of monitoring and auditing by the sponsor, and inspection by local and regulatory authorities.

